2.2. Endpoints

Primary Endpoint(s)

CLUE Comfort and Vision

The primary endpoints are overall quality of vision and overall comfort scores using Contact Lens User Experience (CLUE)TM questionnaire at the two-week follow-up. CLUE is a validated patient-reported outcomes questionnaire to assess patient-experience attributes of soft, disposable contact lenses (comfort, vision, handling, and packaging) in a contact-lens wearing population in the US, ages 18-65. Scores follow a normal distribution with a population average score of 60 (SD 20), where higher scores indicate a more favorable/positive response.

Other Observation(s)

Other endpoints are being evaluated chiefly to design future studies.

1. Driving Performance

Driving performance will be assessed by two individual patient reported outcome (PRO) questions at the 2-week follow-up evaluation. The individual items are as follows:

- A. Reduction in glare while driving during the day (Item ID: MIS00617)
- B. Reduction in glare while driving during the night (Item ID: MIS00618)

2. Indoor Performance

Indoor performance will be assessed by three individual patient reported outcome (PRO) questions at the 2-week follow-up evaluation. The individual items are as follows:

- A. Reduction in glare from the computer screen (Item ID: MIS00628)
- B. Reduction in glare caused by bright indoor lights (Item ID: MIS00625)
- C. Reduction in glare caused by bright light coming through the window (Item ID: MIS00626)

3. Outdoor Performance

Outdoor performance will be assessed by four individual patient reported outcome (PRO) questions at the 2-week follow-up evaluation. The individual items are as follows:

- A. Ability to see comfortably in bright sunlight (Item ID: MIS00613)
- B. Reduction in glare in bright sunlight (Item ID: MIS00614)
- C. Reduction in squinting in bright sunlight (Item ID: MIS00615)
- D. Reduction in eye strain in bright sunlight (Item ID: MIS00616)

All driving, indoor and outdoor (PRO) items above will be assessed using the same excellence scale of; 0: Not Applicable, 1: Excellent, 2: Very Good, 3: Good, 4: Fair and 5: Poor.

4. CLUE Handling

Handling scores will be assessed by using Contact Lens User Experience (CLUE)TM questionnaire at the two-week follow-up.

5. Physiological Response assessed at each visit.

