2.3. Hypotheses

Primary Hypotheses

| Primary Hypotheses | | |
|----------------------|------------------------------------------------------------------------------------------------------------------------------------------------------------------------------------|--|
| Endpoint | Hypothesis | |
| Overall CLUE Vision | The test lens will be non-inferior to the control lens at the 2-week follow-up with respect to CLUE overall quality of vision. A non-inferiority margin of -5 points will be used. | |
| Overall CLUE Comfort | The test lens will be non-inferior to the control lens at the 2-week follow-up with respect to CLUE overall comfort. A non-inferiority margin of -5 points will be used. | |

Both Primary hypotheses must be met for this study to be considered successful.

Other Hypotheses

| | Other Hypotheses | | | |
|---------------------------------|-------------------------------------------------------------------------------------------------------------------------------------------------------------------------------------------------------------------------------------------------------------------------------------------------------------------------------------------------------------------------------------------------------------------------|--|--|--|
| Endpoint | Hypothesis | | | |
| Outdoor Performance Measures | The test lens will be superior to the control lens in at least 2 of the following 4 outdoor performance measure(s) at the 2-week follow-up. An odds ratio margin of 1 will be used. 1. Ability to see comfortably in bright sunlight 2. Reduction in glare in bright sunlight 3. Reduction in squinting in bright sunlight 4. Reduction in eye strain in bright sunlight | | | |
| Driving Performance Metrics | The test lens will be non-inferior to the control lens in both of the following driving performance metrics at the 2-week follow-up. An odds ratio margin of 0.67 will be used. 1. Reduction in glare while driving during the day 2. Reduction in glare while driving during the night | | | |
| Indoor Performance Measures | The test lens will be superior to the control lens in at least 2 of the following 4 outdoor performance measure(s) at the 2-week follow-up. An odds ratio margin of 1 will be used. 1. Reduction in squinting while working on the computer 2. Reduction in glare from the computer screen 3. Reduction in glare caused by bright indoor lights 4. Reduction in glare caused by bright light coming through the window | | | |

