| CLUE Handling | CLUE handling of the step-cure and static cure lenses will be no different from each other. | | | |
| Physiological Response | Physiological responses of the step-cure and static cure lenses will be no different from each other. | | | |

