14.5. Primary Analysis

CLUE Comfort and Vision

Overall comfort and vision CLUE scores will be analyzed separately using a linear mixed model adjusting for baseline values as a covariate. Sequence of lens wear, period, lens type, first order carryover effect will be included in each model as fixed effects. An appropriate covariance structure will be used to model the residual errors between measurements within same subject across study periods (R-side). The covariance structure will be selected based on the finite-sample corrected Akaike's Information Criterion. Covariance structures considered include:

- Unstructured Covariance Structure (UN)
- Homogenous Compound symmetry (CS)
- Heterogeneous Compound Symmetry (CSH)
- Autoregressive first order (AR (1))

For autoregressive first order (AR (1)), Site and Subject nest within site will be included as random effects (G-side). For the remaining covariance structures only site will be included as a random effect (G-side). The Kenward and Roger method (Kenward and Roger, 1997) will be used for the denominator degree of freedom.

Comparisons between the test and control lens at the 2-weeks follow-up will be carried out using two-sided 95% confidence intervals constructed for least-square mean differences (test

minus control). The lower limit of the 95% confidence interval will be compared to -5 and 0 to test for non-inferiority and superiority, respectively. Non-inferiority of the test lens relative to the control will be concluded if a lower limit is above -5. If non-inferiority is established the superiority will be tested. Superiority will be declared if the lower limit of the 95% confidence interval is above 0.

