14.7. Other Exploratory Analyses

Driving, Indoor and Outdoor Performance

Each driving, indoor and outdoor performance item will be analyzed separately using a generalized linear mixed model for ordinal data with a multinomial distribution and cumulative logit as a link function. The experimental design factors: sequence of lens wear, period, lens type, first order carryover effect will be included in each model as fixed effects. Site will be included as a random effect. An appropriate covariance structure will be used to model the residual errors between measurements within same subject across study periods.

The assumption of proportionality of odds across response categories will be assessed graphically. If this assumption is violated then the distribution of responses will be investigated. If sparse data is observed then the sparse response categories may be collapsed to ensure there is sufficient data for analysis. If the assumption of proportionality of odds is still violated in the collapsed categories then a partial proportional odds model may be considered. If any of the above models fail to converge, then reduced versions may be considered. A Generalized Estimating Equation (GEE) may also be considered as necessary.

Comparison between the test lens and the control lens at the 2-week follow-up will be carried out using two-sided 95% confidence intervals of the odds ratios (Test over Control); where the odds ratio represents the odds of having a higher positive rating/experience for the Test lens compared to the Control lens.

For driving items, non-inferiority of the test lens relative to the control will be concluded if the lower limit of the 95% confidence interval of the odds ratio is above 0.67. If non-inferiority is met, then superiority will be tested. Superiority of the test lens relative to the control lens will be concluded if the lower limit of the confidence interval of the odds ratio is above 1.

CLUE Handling

CLUE handling will be analyzed and tested in the same exact manner as CLUE comfort and vision as describe above in Section 14.5.

Physiological Responses will be descriptively summarized for each lens type.

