APPENDIX A: PATIENT REPORTED OUTCOMES (STUDY QUESTIONNAIRES)

2

10

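### Section 2.3 counts four indoor items where Section 2.2 defines three, and its no-difference hypothesis for handling is sent to a lower-limit rule that cannot establish it

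*Combined protocol and SAP*

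**What the plan says.** **Indoor items.** Section 2.2 states that "Indoor performance will be assessed by three individual patient reported outcome (PRO) questions" and lists three, each with an item ID: glare from the computer screen, from bright indoor lights, and from light through a window. The indoor row of the Other Hypotheses table in Section 2.3 requires superiority on at least 2 of "4 outdoor performance measure(s) at the 2-week follow-up. An odds ratio margin of 1 will be used. 1. Reduction in squinting" and so on. Three of its four items match Section 2.2. The other, "Reduction in squinting while working on the computer", is not in Section 2.2 and has no item ID.

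**Handling.** The hypothesis in Section 2.3 is that "CLUE handling of the step-cure and static cure lenses will be no different from each other". Section 14.7 says that "CLUE handling will be analyzed and tested in the same exact manner as CLUE comfort and vision". The rule in Section 14.5 is: "The lower limit of the 95% confidence interval will be compared to -5 and 0 to test for non-inferiority and superiority, respectively".

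**Status.** Section 2.2 says of this group: "Other endpoints are being evaluated chiefly to design future studies". Section 2.3 rests study success on the two primary CLUE hypotheses only.

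**The concern.** For the indoor endpoint, the plan states a success count whose denominator conflicts with its own endpoint definition. The rule can still be applied, because superiority on two of the three defined items already meets 2 of 4. But a fourth item gives an extra chance of reaching two, so the probability of success depends on which section is followed. The content of Appendix A is not shown in the public text, so it cannot be seen there whether the squinting item is on the questionnaire.

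For handling, the hypothesis and the test point in different directions. A claim of no difference needs both confidence limits held inside a stated range. The planned rule looks only at the lower limit, and its second step can only declare that the lenses differ. A pass could therefore be reported as support for a hypothesis that it does not address.

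**Working it through.** No figure in the plan is contested, so the check is a comparison of the sections followed by an illustration of size.

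**1. Indoor items**

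| | Section 2.2 | Section 2.3, indoor row |
|---|---|---|
| Number of items | 3 | 4 |
| Label | indoor | outdoor |
| Computer-screen glare | yes | yes |
| Bright indoor lights | yes | yes |
| Light through the window | yes | yes |
| Squinting at the computer | no | yes |

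The count in Section 2.2 is spelled out as a word and agrees with its list, so missing text does not explain the mismatch.

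Size: let p be the chance that one item shows superiority. The documents give no value, so p is an assumption. For independent items the chance of at least 2 successes is binomial. For correlated items I used equally correlated normal test statistics with correlation ρ.

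| p per item | ρ | 2 of 4 | 2 of 3 |
|---|---|---|---|
| 0.50 | 0 | 69% | 50% |
| 0.50 | 0.5 | 60% | 50% |
| 0.50 | 0.9 | 54% | 50% |
| 0.20 | 0 | 18% | 10% |
| 0.20 | 0.5 | 22% | 16% |
| 0.20 | 0.9 | 22% | 19% |
| 0.025 (true OR 1) | 0 | 0.36% | 0.18% |
| 0.025 (true OR 1) | 0.9 | 2.7% | 2.2% |

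When the lenses do not differ, either count succeeds at most 2.7% of the time in these cases, so false-positive risk is not the issue.

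**2. Handling**

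That the rule cannot show no difference follows from its form and needs no variance. For size, no handling variance is given, so I borrow the compound-symmetric matrices of Section 14.2: variance minus covariance is 349.3 - 110.9 = 238.4 (comfort) and 257.4 - 82.1 = 175.3 (vision).

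Take 80 completers, 40 per sequence, with lens, sequence, period and carryover in the model and no baseline covariate. The lens effect comes from the contrast 2y1 - y2 - y3, whose variance is 6 × (variance - covariance). The difference in this contrast between sequences equals 4 times the lens effect; period and carryover cancel. So

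SE² = 6 × (variance - covariance) × (1/40 + 1/40) / 16 = 1.5 × (variance - covariance) / 80,

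which gives SE = 2.114 (comfort) and 1.813 (vision).

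With true difference d (Test minus Control) and a normal approximation:

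- Lower limit above -5: Φ((5 + d)/SE - 1.96)
- Lower limit above 0: Φ(d/SE - 1.96)
- Both 95% limits within an assumed ±5: Φ((5 - d)/SE - 1.96) - Φ((-5 - d)/SE + 1.96)

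| | d = 0, comfort / vision | d = +5, comfort / vision |
|---|---|---|
| Passes the -5 rule | 66% / 79% | 99.7% / 99.98% |
| Superiority declared | 2.5% / 2.5% | 66% / 79% |
| Both 95% limits within ±5 | 31% / 58% | 2.2% / 2.5% |

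**Link to Table 5.** Table 5 states 93% and 98% power at 80, not 66% and 79%. Its six figures come back to within 1 point if N is read as subjects per sequence with lens as the only fixed effect: comfort 77.4, 84.4, 92.9% (stated 77, 85, 93) and vision 88.5, 93.4, 97.9% (stated 88, 93, 98). At that precision (SE 1.457 and 1.250) the ±5 criterion would pass 86% and 96% of the time at zero difference. The argument about the rule is the same under either reading.

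**The case against.** The indoor row repeats the wording of the outdoor row above it, so a copying slip is a likely explanation. Section 14.7 models each item separately with its own odds ratio and interval, so no model depends on 3 versus 4. Both lenses carry the same UV-blocker and, on the parameters listed in Table 1, differ only in cure technique; the case of no true difference is therefore the most relevant one, and there the two counts differ by half a percentage point or less at the correlations shown. For handling, the interval is two-sided, so a reader will see the upper limit, and if Test were truly 5 points better the superiority step would usually say so. The ±5 criterion is also strict: with 90% limits, which a 5% level could support, it would pass 53% (comfort) and 73% (vision) at zero difference.

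Most of this stands, and it is why the point is minor. It does not remove either defect. Even a slip leaves a stated success count that contradicts the endpoint definition. An upper limit with no decision attached does not test a no-difference hypothesis, and a declared superiority contradicts that hypothesis instead of supporting it.

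**Conclusion.** The concern holds, and it is minor. The indoor row of Section 2.3 is wrong as written: its label is wrong and its item list conflicts with Section 2.2. The choice of denominator moves the chance of success by 4 to 19 percentage points at an assumed 50% per item, and by 3 to 8 points at 20%, depending on correlation. The handling hypothesis cannot be concluded from its planned test. That is a matter of logic; only the percentages rest on the borrowed covariance, the normal approximation and the assumed ±5 range. Neither defect touches the primary success criterion. What is affected is what may be concluded and reported for these exploratory endpoints.

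Two related gaps are missing detail only. Section 14.7 spells out the interval decision for driving items but not for indoor or outdoor items, and it plans only a descriptive summary for the physiological no-difference hypothesis.

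**What to change.** 1. **Indoor.** Reconcile Sections 2.2 and 2.3 with the questionnaire and correct the label to indoor. If three items are collected, delete the squinting item from Section 2.3 and set the rule at 2 of 3. If four are collected, add the squinting item with its ID to Section 2.2 and keep 2 of 4.
2. **Handling.** Restate the hypothesis as non-inferiority with margin -5, which is what Sections 14.5 and 14.7 already test. Keep a no-difference claim only if Section 14.7 adds an upper bound, for example both limits within a justified symmetric range, and states the confidence level.
3. **Minor.** Repeat the indoor and outdoor decision in Section 14.7 (lower odds-ratio limit above 1, with the item count), and word the physiological hypothesis as a descriptive comparison by lens.

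The cost is wording in Sections 2.2, 2.3 and 14.7, with the same models. No new data are needed unless the squinting item is kept and is not already on the questionnaire. The non-inferiority wording costs no power but gives up the no-difference claim. The two-sided alternative would pass only about 31% to 58% of the time at zero difference, using 95% limits, ±5 and 80 completers in total under the borrowed covariance.

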2. STUDY OBJECTIVES, ENDPOINTS AND HYPOTHESES

2.1. Objectives

Primary Objective(s)

The primary objective of this study is to compare the clinical performance of two study contact lenses using different curing techniques with respect to CLUE comfort and vision.

Other Objectives(s)

Other objectives of this study are to compare the clinical performance of two study contact lenses using different curing techniques with respect to driving, indoor and outdoor performance items, CLUE handling and the rate of Grade 3 or higher slit lamp findings.

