3. TARGETED STUDY POPULATION

3.1. General Characteristics

Approximately 90 subjects will be enrolled to ensure that at least 80 subjects will complete the study. Enrolled subjects will be habitual wearers of spherical contact lenses. All subjects will be the age of 18 or older. Eligible presbyopes will be those that wear full distance contact lenses in both eyes, then wear reading glasses over them. Subjects will wear the test and control contact lenses approximately two weeks each on a daily wear (DW) basis, then wear either the test or control lens again for two weeks, for a total study duration of approximately 42 days (6 weeks) per subject.

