4. STUDY DESIGN AND RATIONALE

4.1. Description of Study Design

This study is a randomized, 4-visit, double-masked, 2x3 bilateral crossover, dispensing trial. Approximately 90 subjects will be screened and enrolled to ensure that at least 80 subjects to complete.

The study begins with an initial visit (Visit 1). If a subject is found to meet all eligibility criteria, they will be random to one of two lens wear sequences (Test/Control/Control or Control/Test/Test).

If the subject is dispensed study lenses at the initial visit, 3 follow-up visits will be conducted. The follow-up visits occur approximately 2, 4 and 6 weeks after the initial visit. Unscheduled follow-up visits may occur during the study. Subjects will be advised to wear the study lenses at least five (5) days per week for at least six (6) hours per day for a period of two weeks each. Lens replacement is scheduled at 2 and 4-week follow-up visits.

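### Section 2.3 hypothesises no difference in physiological response between the two cures, but Section 14.7 plans only per-lens description, which cannot support that statement

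*Combined protocol and SAP*

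**What the plan says.** Section 2.1 lists, among the other objectives, a comparison of the two lenses on "the rate of Grade 3 or higher slit lamp findings". The last row of the other-hypotheses table in Section 2.3 states that "Physiological responses of the step-cure and static cure lenses will be no different from each other". That row names no grade, summary measure, margin or time point. Section 2.2 lists physiological response as an endpoint assessed at every visit.

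The analysis is a single sentence at the end of Section 14.7: "Physiological Responses will be descriptively summarized for each lens type". Section 14.1 says what such a summary contains: n, mean, SD, median and range for continuous variables, and counts and percentages for categorical ones. The sample size in Section 14.2 rests on CLUE comfort and vision alone.

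**The concern.** A statement that two lenses do not differ needs at least an estimate of the difference and a measure of how large a difference the data leave open. Section 14.7 supplies neither. Whether the hypothesis held would be left to someone reading two columns of a table, with no stated standard.

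This row stands alone. The primary rows in Section 2.3 each carry a margin ("A non-inferiority margin of -5 points will be used"). The driving, indoor and outdoor items have odds-ratio margins, and Section 14.7 gives them 95% intervals. CLUE handling is sent to the confidence-interval method of Section 14.5. Only physiological response has a comparative hypothesis with no comparative analysis.

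What is at stake is the accuracy of one exploratory statement in the report. Grade 3+ findings are an exclusion at entry (Section 3.3, criterion 11), so counts are probably small, and similar small counts say little about whether the rates are the same.

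**Working it through.** **Plan's own figure.** There is none to reproduce. The documents give no expected Grade 3+ rate, margin or power for this endpoint. The rates and margins below are assumptions, used only for illustration.

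**Denominator.** Section 3.1: "Approximately 90 subjects will be enrolled to ensure that at least 80 subjects will complete the study". Section 4.1 assigns subjects to "one of two lens wear sequences (Test/Control/Control or Control/Test/Test"), so every completer wears both lenses. The Safety Population (Section 14.3) is everyone given a test article. If the targets are met, the number exposed to each lens lies between about 80 (completers) and about 90 (all enrolled). Completers alone are the wrong set: under steps 2.11 and 3.11 of Section 7.2, a subject with a Grade 3 or 4 finding at Visit 2 or 3 is followed and then leaves the study, and so is not a completer.

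**What an empty cell leaves open on one lens.** With 0 events in n subjects, the exact two-sided 95% upper limit is 1 − 0.025^(1/n).
- n = 80: 1 − 0.025^(1/80) = 4.5%
- n = 90: 1 − 0.025^(1/90) = 4.0%

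**What equal counts leave open for the difference.** Newcombe 95% interval, treating the lenses as independent. For 0 against 0 the half-width is the Wilson upper limit, z²/(n + z²), with z² = 3.841.
- 0 v 0: 3.841/83.841 = ±4.6 points at n = 80; 3.841/93.841 = ±4.1 points at n = 90
- 1 v 1: ±5.6 points at 80; ±5.0 at 90
- 2 v 2: ±6.4 points at 80; ±5.8 at 90

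**Is that enough?** It depends on a margin that the plan does not state. With equal true rates p, margin m, one-sided 2.5% and 80% power, the normal approximation gives n per lens = (1.960 + 0.842)² × 2p(1 − p)/m², where the first factor is 7.849.
- p = 1%, m = 5 points: 7.849 × 0.0198/0.0025 = 62.2, so 63
- p = 2%, m = 5 points: 7.849 × 0.0392/0.0025 = 123.1, so 124
- p = 1%, m = 2 points: 7.849 × 0.0198/0.0004 = 388.5, so 389
- p = 5%, m = 10 points: 7.849 × 0.095/0.01 = 74.6, so 75

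So 80 to 90 subjects would be adequate for some combinations and far short for others.

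**Would a real excess show in the table anyway?** Exact binomial calculation, n = 80, lenses independent:

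| True rate, Control v Test | Test count no higher than Control | Counts within 1 of each other | Test higher by 2 or more |
|---|---|---|---|
| 1% v 3% | 27% | 47% | 50% |
| 1% v 5% | 9% | 21% | 79% |
| 2% v 8% | 5% | 10% | 89% |
| 2% v 10% | 2% | 4% | 96% |

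A large excess would usually be visible. A moderate one at low rates often would not be.

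**The case against.** The strongest reply is that the row is exploratory by design. Section 2.2 says that "Other endpoints are being evaluated chiefly to design future studies", Section 2.3 that "Both Primary hypotheses must be met for this study to be considered successful", and the Synopsis links the eventual lock on the curing method to comfort and quality of vision. Grade 3 and 4 findings are also followed individually as adverse events, and describing rare events is normal practice. All of this stands. It limits the importance of the point but does not repair the mismatch: a descriptive plan fits a descriptive objective, not a hypothesis of no difference. Planning later studies also calls for estimates with intervals.

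A reader might infer three stronger things that the documents do not support.

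- *That a clean or balanced table is the likely result even if the static-cure lens has a several-fold higher Grade 3+ rate.* At the assumed rates above, the Test count exceeds Control by 2 or more in 50% to 96% of trials.
- *That this sample cannot support any statement about Grade 3+ findings.* That depends on a rate and a margin that the documents do not give; for some values 80 would suffice.
- *That the study's conclusion or the curing decision rests on this row.* No section says so, and no section gives a rule for declaring the row met.

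Two objections to possible remedies also stand. A paired analysis (McNemar, or an exact paired interval) on completers would fail: a subject who exits with an event in period 1 never wears the other lens and has no pair. And the Section 14.5 model was written for one CLUE score per subject per period, so it cannot be applied unchanged to findings graded in each eye.

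**Conclusion.** The mismatch holds as a minor point, worth considering. As written, the plan has no between-lens estimate or interval for physiological response and so cannot support its own hypothesis of no difference. The primary CLUE conclusion is untouched.

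The illustration is that no Grade 3+ events in 80 to 90 exposed subjects leaves a true rate of up to about 4.5% to 4.0% open on that lens, and about ±4.6 to ±4.1 points open for the difference if both lenses are clean. The per-lens limit assumes only independent subjects and the planned enrolment. The limits for the difference also treat the two lenses as independent within subject.

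**What to change.** 1. In Section 2.3, replace the physiological-response hypothesis with an estimation objective, and state that no equivalence is claimed.
2. In Section 14.7, for Grade 3+ findings, report the number of subjects with any such finding on each lens in the Safety Population. Use those exposed to that lens as the denominator and include subjects who exit early. Give exact 95% limits per lens and a 95% interval for Test minus Control by a method that does not require complete pairs.
3. In Section 14.7, for the expanded redness and corneal staining grades, report the Test-minus-Control difference with its 95% interval from a crossover mixed model like that in Section 14.5, extended to two eyes per subject by an eye-level term or a subject-level summary.

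The data are already scheduled in Table 3 (Section 7.1), so no subjects, visits or procedures are added. The cost is some rewording and a little more analysis work, and the eventual safety statement will read less favourably: it will name the excess that the data do not exclude. The change is best made before the data are seen, since Section 14.10 requires a later change to be documented and justified in the study report.
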